9.1 Potential Benefits to Participants and Others

9.1.1 Participants

The opportunity to assist in the advancement of sleep-in-pregnancy knowledge and the possibility of benefiting other pregnant women in their community, country, and region in the future may be a source of immediate satisfaction to participants.

9.1.2 Others

In Canada, three babies are stillborn every day ($\geq 1000\text{g}$ birthweight or ≥ 28 weeks completed gestation) (1). This is a largely unrecognized national issue yet pales in comparison to Ghana, where 47 babies are stillborn every day (1). In addition, every day, 61 Canadian babies are born with LBW ($\leq 2500\text{g}$) (26), and 232 Ghanaian babies are born with LBW (20) – many of whom will die in infancy or suffer lifelong consequences.

If maternal back sleep has a causative role in LBW and subsequently SB, the population attributable risk (PAR%) suggests that up to 17% of LBW, and consequently 26% of SB, might be averted by changing maternal sleep position (18) – this translates to the potential global aversion of 3.7 million LBW and 676,000 SB annually (1) (2). Since LBW is a major contributor to SB (3), morbidity (2) (9) (10), and neonatal mortality (60-80%) (4) (5) (6) (7), further benefit may be realized.

The results of this study will be imperative for interpretation of the results of the Ghana PrenaBelt Trial (GPT), which is a study testing a novel approach to reducing the global incidence of SB and LBW. Demonstrating that back-sleep education does (or does not) improve pregnancy outcomes (e.g., birth weight) will be a valuable contribution to existing knowledge and may be a key component to reducing the rates of SB and LBW in Ghana and worldwide.

Currently, research is underway to determine whether a causal relationship between maternal sleep position and SB and LBW exists and collect a robust evidence base from which to advise whether a public health intervention should be considered (dissemination of research findings expected by August 2016) (22). If a public health intervention is advised, our studies (Ghana PrenaBelt Trial and KBTH-GIRHL Healthy Birth Weight Study) taken

together will be at the forefront of scientific investigation into two possible interventions, i.e., back-sleep education and positional therapy.

9.2 Potential Harms to Participants and Others

This study is minimal risk. Participants in this study are at no greater risk of harms when completing the activities of this study (Data Collection Questionnaire) than those risks they encounter in their everyday life.

Since personal health information will be collected from participants, there always exists the potential harm should breach of confidentiality inadvertently occur.

9.3 Minimization of Potential Harms

Personal health information (PHI) used to identify potential participants will not be accessed by anyone other than the KBTH study personnel within their circle of care.

Upon enrolment in the study, each participant will be assigned a random, six-digit, alphanumeric code. All data collected from participants during the studies will be collected only in association with this code, thus automatically de-identifying the data and minimizing the risk of identification. The key to the code, which links the codes to the patients' KBTH hospital record number, will be kept in a secure location away from the de-identified study data and destroyed at the earliest possible time after it is no longer needed for study purposes, thus minimizing the risk of re-identification. The de-identified data in forms (paper) and files (electronic) will be secured in a locked filing cabinet in a locked office with limited access and on the secure, password-protected, Microsoft OneDrive cloud, respectively.

For all study activities, all data collected from participants will be protected from unauthorized access to safeguard participant privacy and confidentiality in accordance with Tri-Council Policy Statement (TCPS 2) and personal information policies at the Korle Bu Teaching Hospital.

Study data will only be exchanged in de-identified form and between study team members authorized by the Principal Investigator. Data will be protected in electronic transfers through password protection and encryption if deemed necessary.

After study closure, study data will be stored securely (locked cabinets, password-protected files, password-protected computers, locked offices) in de-identified form for five

years, after which it will be destroyed in a secure manner (e.g., incineration and cross-cut shredding).

9.4 Process for Seeking Consent

1. **Ethical Approval and Training:** This study requires approval from the Korle Bu Teaching Hospital Institutional Review Board (Accra, Ghana). All study personnel will be trained to the approved Research Protocol by [name] (Principal Investigator).
2. **Recruitment:**
 - Study personnel (KBTH staff person) within the circle of care of patients who delivered a live baby at the KBTH Obstetrics and Gynaecology Department within the past 48 hours will visit the wards to invite patients to join the study. In an effort to avoid selection bias, the study personnel will visit the wards daily in the morning (before patients are discharged) and 100% of patients will be approached and invited to participate in the study – this will occur until the target sample size for the study is reached. Patients who are interested in joining the study will then be screened by the study personnel using the approved Screening Inclusion Form to determine if they meet the inclusion/exclusion criteria for this study. Note that only study personnel that are within these patients' circle of care will access their patients' health records. Researchers on the study team who are not within the circle of care will not access the patients' health records.
 - Patients who meet the inclusion/exclusion criteria will be invited to participate in the study by the study personnel within the circle of care. If a patient is interested in participating, the study personnel will conduct the consent process using the approved Information and Consent Form.
3. **Consent:**
 - Potential participants, having
 - met the study inclusion/exclusion criteria,
 - been invited to participate in the study, and
 - shown express interest in participating in the studywill meet with study personnel to complete the consent process.

- In the meeting, the study personnel will go through the approved Information and Consent Form with the potential participant ensuring full and accurate disclosure of the,
 - nature of the study (what is involved, who will be conducting it, how the results will be used, how confidentiality and privacy will be protected),
 - risks and benefits involved in participating in the study, and
 - free choice to decline participation in or withdraw from the study at any time without consequence (no adverse or negative effect on her or her family's care in any way; her de-identified data up to the point of withdrawal will be retained by the study team)
- The capacity of each potential participant to provide consent will be assessed by the study personnel by asking the potential participant questions to verify she understands the information relevant to giving or refusing consent and appreciates the outcomes of both choices:
 - a. What is this study about?
 - b. Why is this study important?
 - c. What will you need to do in this study?
 - d. What are the risks to you from being involved in this study?
 - e. What are the benefits to you from being involved in this study?
 - f. What happens if you choose to not participate today?
 - g. What happens if you choose to participate today and then change your mind at another time and choose to not participate?
- The study personnel will give each potential participant an opportunity to ask any questions she may have.
- Voluntary, written (or participant's thumb print along with the signature of an impartial witness if the potential participant is not English literate), informed consent will be obtained with the participant's contact information by the study personnel from a potential participant who has demonstrated capacity and maintains an interest in enrolling in the study. When the Information and Consent Form is signed, the participant will be enrolled in the study and assigned a six-

digit, alphanumeric code for the purposes of de-identifying all data collected from her while enrolled in the study.

- Authorization or refusal of consent by a potential participant will be accepted by the study personnel.
- The Informed Consent Form is the source documentation of the informed consent process. The original, signed, and dated consent will be placed in the secure files of the Principal Investigator.

10 Timeline/Work Schedule

March-July 2016: Obtain ethics approval from KBTH-IRB for the KBTH-GIRHL Healthy Birth Weight Study

July-November 2016: Conduct the KBTH-GIRHL Healthy Birth Weight Study (chart reviews, questionnaires)

December 2016: Analyze data from the KBTH-GIRHL Healthy Birth Weight Study in conjunction with data from the Ghana PrenaBelt Trial.

Table 2 – Study Personnel

Name	Role
[name]	As Principal Investigator, he will conduct screening of potential participants and consent for questionnaire and hospital chart review. He will also conduct data capture (via Data Collection Questionnaire and Delivery Outcome Form) and storage (via OneDrive cloud).

13.1 Screening Inclusion Form

Attached.

13.2 Information and Consent Form

Attached.

13.3 Data Collection Questionnaire

Attached.

13.4 Delivery Outcome Form

Attached.

13.5 Principal Investigator CV

Attached.

Cover Page

Statistical Analysis Plan

Official Title: Korle Bu Teaching Hospital - Global Innovations for Reproductive Health & Life
Healthy Birth Weight Study: A Cross-Section

NTC03062228

Document Date: 20JUL2016

Statistical Analysis Plan

1. Designation of Personnel

All analyses described will be performed by the Project Lead and Co-Investigator, [name], under the supervision of the consulting statistician, [name]. The analyses described will be performed using the R statistical software package (version 3.2.0., “Full of Ingredients”).

2. Outcome measurements

Primary Outcomes:

- Birth weight
- Customized birth weight centile

Secondary outcomes:

- Gestational Age at Delivery
- Small for Gestational Age
- Low Birth Weight
- Sex of Newborn
- Preterm Delivery
- Mode of Delivery

3. Sample size calculation

A sample size of one-hundred sixty-two (N=162) participants is selected for the KBTH-GIRHL Healthy Birth Weight Study. N=162 is the minimum combined group size for the Ghana PrenaBelt Trial (NTC02379728): n=81 treatments plus n=81 sham-controls. The Ghana PrenaBelt Trial sample size was statistically justified (using power of 0.8 and type I error probability of 0.05 and accounting for 20% lost to follow up) based on a previous study in a Ghanaian population by members of our team ([name], [name]) and using the PS Power and Sample Size Program (Version 3.0).

In order to avoid variance bias in comparison of the non-educated (KBTH-GIRHL Healthy Birth Weight Study) group to the back-sleep educated group (Ghana PrenaBelt Trial), the group sizes should be the same; therefore, one-hundred sixty-two (N=162) participants will be included in this study to match the 162 (minimum) participants in the Ghana PrenaBelt Trial. Since this is a cross-sectional study to recruit a control group only, no participants in this study will be lost to follow up; therefore, 162 participants are required in this study.

4. Treatment randomization

Not applicable. This is a cross-sectional study; therefore, no randomization is performed.

5. Interim safety analysis

Not applicable.

6. Analyses at study termination

Descriptive statistics will be employed for collected demographic, obstetric, and sleep habits information from the Data Collection Questionnaire and outcome measures from the Delivery Outcome Form.

Interpretation of the results from this study will be conducted in conjunction with results from the Ghana PrenaBelt Trial as follows:

- Comparison of groups (back-sleep education, no back-sleep education):
 - For continuous variables, the assumption of normality will be assessed using Q-Q plots and the Anderson-Darling test.
 - If normal, paired t-test will be used for evaluating differences.
 - If non-normal, Wilcoxon signed rank test will be used for evaluating differences.
 - For dichotomous and categorical data, we will evaluate for differences using Chi-squared, Fisher's exact test, or McNemar's test for repeated measurements.
- Note that all analyses will be conducted via the intention-to-treat approach in order to provide unbiased comparisons among treatment groups.

Central quantitative data will be sorted and stored in Microsoft Excel files. Quantitative data analysis will be performed in the R statistical software. We will report the number of participants with missing data.

7. Deviation from outlined statistical plan

All analyses will be performed as outlined above. Any deviation from this plan will only be done so under the guidance of the consulting statistician, [name], who will give written justification for the modification from the protocol. A description of the changes and justification for such will be available to regulatory and ethics authorities.

[name]
Project Lead, Co-Investigator
GIRHL

[name]
Consulting Statistician
Nova Scotia Trauma Program

[name]
Principal Investigator
Korle Bu Teaching Hospital

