1.2 Rationale

At the half-way point in the Ghana PrenaBelt Trial (“GPT”) (n=41 births in each group), no difference in birth weight was found between the two groups (PrenaBelt versus sham-PrenaBelt) on a two-sample t-test (p=0.51). Conclusions were the same using a non-parametric method (Wilcoxon rank sum test). Note that hypothesis for the GPT is that the birth weights will be higher in the PrenaBelt group than in the sham-PrenaBelt group.

The GPT was originally proposed as a randomized controlled trial with a treatment (PrenaBelt) group and a control (no PrenaBelt) group; however, the Noguchi-IRB strongly recommended that the study be sham-controlled and double blinded. Our team elected to follow the IRB’s recommendation.

In the GPT, participants are educated on the rationale for the study as part of the informed consent process, i.e., back sleep in late pregnancy has been recently implicated as a possibly modifiable risk factor for stillbirth and low birth weight. Participants are subsequently randomized to receive treatment with a PrenaBelt or a sham-PrenaBelt and are blinded to their treatment allocation.

Given the results of the interim analysis, it is questioned if the back-sleep education during the consent process could be having an effect on the sleep behaviour of the participants independently of their treatment allocation. The GPT Team reports that the education could be having an effect, for example, some participants in the sham-PrenaBelt group have reported that they stopped using their assigned device because they had since trained themselves to sleep exclusively on their left side using alternative means.

Many campaigns have had unprecedented impact on public health by education alone, for example, the “back-to-sleep” campaign to prevent sudden infant death syndrome. Therefore, since both the PrenaBelt (treatment) and sham-PrenaBelt (sham-control) groups have received back-sleep education, our team contends that an investigation of a third group without back-sleep education, a true control group, is warranted for comparison.

2 Research Question

What is the mean birth weight and standard deviation of babies born to a cohort of women who:

- Meet the same inclusion/exclusion criteria as the cohort in the Ghana PrenaBelt Trial,
- Have not received education that back sleep during late pregnancy is a possible modifiable risk factor for low birth weight and stillbirth,
- Did not participate in the Ghana PrenaBelt Trial, and

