5.4 Sample Size Determination

A sample size of one-hundred sixty-two (N=162) participants is selected for the KBTH-GIRHL Healthy Birth Weight Study. N=162 is the minimum combined group size for the Ghana PrenaBelt Trial: n=81 treatments plus n=81 sham-controls. The Ghana PrenaBelt Trial sample size was statistically justified (using power of 0.8 and type I error probability of 0.05 and accounting for 20% lost to follow up) based on a previous study in a Ghanaian population by members of our team ([name], [name]) (18) and using the PS Power and Sample Size Program (Version 3.0).

In order to avoid variance bias in comparison of the non-educated (KBTH-GIRHL Healthy Birth Weight Study) group to the back-sleep educated group (Ghana PrenaBelt Trial), the group sizes should be the same; therefore, one-hundred sixty-two (N=162) participants will be included in this study to match the 162 (minimum) participants in the Ghana PrenaBelt Trial. Since this is a cross-sectional study to recruit a control group only, no participants in this study will be lost to follow up; therefore, 162 participants are required in this study.

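### The education comparison pools PrenaBelt and sham women, so it carries about half of any device effect; no sham-only birth-weight contrast is planned

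*SAP*

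**What the plan says.** SAP section 6 and Protocol section 7 list a single comparison: "Comparison of groups (back-sleep education, no back-sleep education". That line does not itself merge the GPT arms. The merging comes from the sample-size text. Protocol 5.4 states that "N=162 is the minimum combined group size for the Ghana PrenaBelt Trial: n=81 treatments plus n=81 sham-controls", and SAP section 3 describes the "comparison of the non-educated (KBTH-GIRHL Healthy Birth Weight Study) group to the back-sleep educated group (Ghana PrenaBelt Trial").

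Other text suggests that three groups were in view:

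- Protocol 1.2 argues that "an investigation of a third group without back-sleep education, a true control group, is warranted for comparison".
- Protocol 3.1, objective 2, names the treatment and sham groups separately, but for questionnaire data. Birth weight falls under objective 1.
- The closing note of SAP section 6 refers to an "intention-to-treat approach in order to provide unbiased comparisons among treatment groups".

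SAP section 6 also says "Interpretation of the results from this study will be conducted in conjunction with results from the Ghana PrenaBelt Trial as follows". What follows is only the two-group comparison and the intention-to-treat note.

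**The concern.** The Protocol summary says that this study and the GPT together will show whether back-sleep education affects birth weight. Half of the educated group also wore the active device, which the GPT was run to test: "Note that hypothesis for the GPT is that the birth weights will be higher in the PrenaBelt group than in the sham-PrenaBelt group". If the device raises birth weight, the pooled contrast credits part of that gain to education. If it lowers birth weight, the contrast hides part of any benefit of education. Education and device are the two interventions that the investigators want to tell apart (Protocol 9.1.2).

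Sham women received the education without the active device, so they are the more direct comparison. The plan never says that they will be compared with the non-educated group on birth weight. Nor does it say how the pooled result is to be read when the GPT device result is, or is not, null.

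**Working it through.** **Inputs from the documents**

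- Educated group: 81 + 81 = 162 as a minimum. No-education group: 162 (Protocol 5.4, SAP 3).
- GPT size: 200 (Protocol 1.1), so up to 100 per arm.
- GPT design: power 0.8, type I error 0.05 (Protocol 5.4). Sidedness is not given.
- GPT interim result: 41 births per arm, p = 0.51 (Protocol 1.2).

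**Assumptions.** No device effect or SD is given, so the device effect D and education effect E are in SD units and D is varied. Tests are two-sided 5% independent-samples t-tests with a common SD (non-central t), not the planned paired test, because the groups are unrelated women.

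**1. The plan's own figure.** 81 + 81 = 162 reproduces as a sum. The 81 per arm cannot be re-derived without a difference and SD. Solving backwards, 81 v 81 has 80% power at 0.443 SD.

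**2. What the pooled contrast estimates.** Let E be educated sham minus non-educated.

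Pooled difference = [81·E + 81·(E + D)] / 162 = E + 0.5·D

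If 81 and 100 are analysed in the two arms, the device weight is 81/181 = 0.448 or 100/181 = 0.552.

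**3. Precision.**

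- Pooled, 162 v 162: SE = √(1/162 + 1/162) = 0.111 SD; 80% power at 0.312 SD.
- Sham only, 81 v 162: SE = √(1/81 + 1/162) = 0.136 SD; 80% power at 0.383 SD. Power at 0.312 SD is 63%.

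**4. Consequence of pooling.** The non-centrality from the device is (D/2)/0.111. The error of the pooled estimate about E is centred on D/2 whatever E is, so coverage of E is one minus the rejection rate at E = 0. With equal arms the pooled mean and the arm difference are independent, so the joint column is pooled rejection × (1 − GPT power).

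| D (SD) | Pooled test rejects, E = 0 | Pooled 95% CI covers E | GPT power for D | Pooled significant, GPT not | Excess over D = 0 |
|---|---|---|---|---|---|
| 0 | 0.050 | 0.950 | 0.050 | 0.0475 | – |
| 0.1 | 0.073 | 0.927 | 0.097 | 0.066 | 0.019 |
| 0.2 | 0.146 | 0.854 | 0.244 | 0.110 | 0.063 |
| 0.3 | 0.270 | 0.730 | 0.475 | 0.142 | 0.094 |
| 0.443 | 0.511 | 0.489 | 0.800 | 0.102 | 0.055 |

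Simulation (40,000 runs per D) gives pooled rejection of 0.049, 0.070, 0.145, 0.268 and 0.499. The gap in the last row reflects the small extra variance from mixing two arms with different means. With unequal arms, rejection at D = 0.3 is 0.236 (weight 0.448) or 0.333 (weight 0.552).

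**5. The other direction.** With E = 0.312 and D = −0.2, the expected pooled difference is 0.312 − 0.100 = 0.212 SD. Pooled power falls from 80% to 48%, against 63% for sham v no education.

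**6. When pooling is still the better estimate.** Mean squared error in SD² is 0.01235 + D²/4 pooled and 0.01852 sham only. They are equal at D = 2·√(0.01852 − 0.01235) = 0.157 with 81 per arm, and at 0.141 with 100 per arm.

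**7. What the interim result implies.** p = 0.51 on 80 degrees of freedom gives |t| = 0.662, so |d| = 0.662 × √(2/41) = 0.146 SD. The 95% half-width is 0.440, giving −0.29 to 0.59 or its mirror image. At D = 0.146 the pooled mean squared error is 0.01235 + 0.00533 = 0.0177, against 0.0185.

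**The case against.** **The pooling is inferred.** SAP section 6 never says how the GPT arms enter, and several phrases point to three groups. This stands as a description, but none of those phrases states a sham-only birth-weight contrast, and the sample-size text is explicit about the combined group.

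**Pooling fits the premise.** The study was prompted by a null interim device result and by sham women training themselves to sleep on the left. If education moved both arms, the device may add little, and pooling then gains precision. At the interim estimate pooling has the slightly lower mean squared error. This stands, and it is why the pooled contrast should be kept. It does not settle the matter, because the interim interval extends to 0.59 SD.

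**The worst figures are where the GPT would raise the alarm.** At 0.443 SD the GPT detects the device 80% of the time. Read jointly, the excess is 2 to 9 points, and about 4 points at 0.146 SD (8.5% v 4.75%). The loss-of-power example needs a device that lowers birth weight, against the GPT hypothesis. This also stands: joint reading lowers the risk without removing it, and the plan gives no rule for that reading.

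**Sham only does not isolate education.** Sham wear, trial participation and non-random recruitment remain. Correct; the proposed wording has to say so.

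**The formal aim is descriptive.** The reference mean and SD are untouched. True, but both documents also plan the group comparison, and birth weight is a primary outcome in the SAP.

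**Conclusion.** The point holds and should be fixed. As written, the planned birth-weight contrast estimates education plus about half of any device effect: exactly half with equal arms, 0.45 to 0.55 if 81 and 100 are analysed. That such a contrast is planned without a sham-only companion or an interpretation rule rests on the text and is secure, as far as these two documents go; the GPT's own plan was not available.

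The practical harm is conditional. It is nil for an inert device, modest at 0.1 SD, and large near 0.443 SD, where the pooled interval would miss the education effect about half the time. For scale, with an assumed SD of 400 to 600 g, a 0.44 SD device effect would put 0.22 × SD, or 88 to 132 g, into the education difference. Which contrast should be the main one is a genuine trade of bias against precision. Leaving that choice unstated is the fault, not pooling as such.

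**What to change.** In SAP section 6 and Protocol section 7, state:

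- Birth weight, and customized centile where the GPT has it, will be summarised for three independent groups: no education, GPT sham, GPT PrenaBelt.
- Sham v no education and GPT combined v no education will both be reported with 95% CIs, beside the GPT PrenaBelt v sham estimate and CI.
- Independent-samples methods (t-test or Wilcoxon rank-sum) will be used. The present text ("If normal, paired t-test will be used for evaluating differences", otherwise signed rank) needs pairs, and these groups have none.
- The combined contrast includes part of any device effect. Neither contrast will be called an effect of education alone, because sham wear, trial participation and non-random recruitment (26–30 weeks' gestation v within 48 hours after a live birth) remain in both.
- The main contrast will be named before the joint analysis. The other is supportive: an estimate with CI and no separate significance claim.

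The cost is rewording and one added contrast. Birth weight needs no new data: the GPT arm is known from randomisation, and GPT data collection ended on 25JUN2016, before the joint analysis planned for December 2016. The documents do not show that the GPT holds customized centile. The statistical price is the wider sham-only interval, which is the reason to report both. Because arm-level interim results were already known, the choice of main contrast should be dated and justified in writing.

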- Gave birth to their babies in a similar time period (year 2016) as the Ghana PrenaBelt Trial?

3 Aims

To establish a reference birth weight (mean and standard deviation) of babies born to a cohort of women comparable to the cohort in the Ghana PrenaBelt Trial but who have not received back-sleep education, did not participate in the Ghana PrenaBelt Trial, and whose babies were born in a similar time period and weighed on the same newborn scales. This reference birth weight will serve as a control for the Ghana PrenaBelt Trial.

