All study personnel involved in off-site data handling and data quality monitoring ([name], [name]) have completed Tri-Council Policy Statement (TCPS-2) training within the past two years. In addition, [name] has completed Good Clinical Practice (GCP) training for investigators from the Collaborative Institutional Training Initiative (CITI) Program within the past two years.

See Section 9.3 Minimization of Potential Harms for measures in place to ensure data security and protect participant privacy and confidentiality.

7 Statistical Analysis

Descriptive statistics (mean, median, standard deviation, maximum, minimum) will be employed for collected demographic, obstetric, and sleep habits information from the Data

Collection Questionnaire and key measurements (e.g., birth weight, gestational age at delivery) from the Delivery Outcome Form.

Interpretation of the results from this study will be conducted in conjunction with results from the Ghana PrenaBelt Trial (GPT) as follows:

- Comparison of groups (back-sleep education, no back-sleep education):
 - For continuous variables, the assumption of normality will be assessed using Q-Q plots and the Anderson-Darling test.
 - If normal, paired t-test will be used for evaluating differences.
 - If non-normal, Wilcoxon signed rank test will be used for evaluating differences.
 - For dichotomous and categorical data, we will evaluate for differences using Chi-squared, Fisher's exact test, or McNemar's test for repeated measurements.
- Note that all analyses will be conducted via the intention-to-treat approach in order to provide unbiased comparisons among treatment groups.

Central quantitative data will be sorted and stored in Microsoft Excel files. Quantitative data analysis will be performed in the R statistical software. We will report the number of participants with missing data.

Any deviations from the original statistical plan will be done under the supervision of our consultant statistician on the GPT ([name], M.Sc. Statistics, MD Candidate 2018) and described in full and justified in the final report, as appropriate.

8 Dissemination of Results

Since the results of this study will be interpreted and presented in conjunction with the results of the Ghana PrenaBelt Trial (GPT), we will follow the dissemination plan of the GPT:

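### An unspecified normality check chooses the test for both primary outcomes, so the primary comparison is not fixed in advance and may not concern means

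*SAP*

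**What the plan says.** SAP section 6 and Protocol section 7 carry the same rule for comparing the educated and non-educated groups. For continuous variables, "the assumption of normality will be assessed using Q-Q plots and the Anderson-Darling test". Then: "If normal, paired t-test will be used for evaluating differences". Otherwise: "If non-normal, Wilcoxon signed rank test will be used for evaluating differences".

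SAP section 2 lists two primary outcomes, birth weight and "Customized birth weight centile". Both are continuous, so both fall under the rule.

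The research question (Protocol section 2) is framed in means: "What is the mean birth weight and standard deviation of babies born to a cohort of women who" meet the listed conditions. The aim (Protocol section 3) adds: "This reference birth weight will serve as a control for the Ghana PrenaBelt Trial". Protocol section 7 also states, ahead of the normality rule and independently of it: "Descriptive statistics (mean, median, standard deviation, maximum, minimum) will be employed", with birth weight named among the key measurements.

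On size, SAP section 3 says "one-hundred sixty-two (N=162) participants will be included in this study to match the 162 (minimum) participants in the Ghana PrenaBelt Trial".

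**The concern.** The two branches do not test the same thing. A t-test compares means; a rank test in general does not. The plan lets the outcome data decide which is used, and leaves three parts of that decision open:

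- the Anderson-Darling significance level;
- the data being tested (each group, the pooled sample or differences);
- what is done when the Q-Q plot and the test point different ways.

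Two analysts following the plan could reach different primary tests from the same data. On the non-normal branch, a study set up to provide a reference mean would have no formal comparison of means. On neither branch does the plan call for the mean difference with a confidence interval, which is the quantity a control group would be expected to yield.

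The same lines have a second fault. Both named tests are paired, yet the non-educated women and the GPT women are different people and no matching is described. Removing the normality check alone would leave a paired t-test on independent groups.

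**Working it through.** **Inputs from the documents.** The non-educated group has n = 162. The educated group has at least 81 + 81 = 162 (SAP section 3), out of N = 200 in the GPT (Protocol section 1.1). No effect size, SD or birth-weight distribution is given, so the figure of 81 per group cannot be re-derived. With two-sided alpha 0.05 (sidedness assumed) and power 0.80, the detectable difference is (1.960 + 0.842) × √(2/n) SD:

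- n = 81: 2.802 × 0.1571 = 0.44 SD
- n = 162: 2.802 × 0.1111 = 0.31 SD

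**Assumptions.** Anderson-Darling (AD) is used at the 5% level with estimated mean and SD. All distribution shapes are assumed. The gated procedure is taken as Welch if both groups pass AD and the unpaired rank-sum test otherwise.

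**Check 1: how often the check diverts the analysis.** Simulation with 162 per group, term weights 3150 ± 430 g and preterm weights 2250 ± 500 g. If p is the rejection rate in one group, the rate in at least one of two independent groups is 1 − (1 − p)².

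| Preterm share | AD rejects, one group | 1 − (1 − p)² | Simulated, at least one group |
|---|---|---|---|
| 5% | 27% | 1 − 0.73² = 47% | 47% |
| 8% | 43% | 1 − 0.57² = 68% | 67% |
| 12% | 58% | 1 − 0.42² = 82% | 82% |

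If AD is applied to differences between arbitrary pairs, rejection falls to about 8%-11% for the same mixtures. The branch taken therefore depends heavily on a choice the plan does not state.

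In these mixtures type I error was 4.4%-6.2% for ungated Welch and 4.4%-5.5% for the gated procedure, with Monte Carlo error of about ±1 point.

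**Check 2: other shapes.** 4000 replicates, 162 per group. The Monte Carlo margin at 5% is 1.96 × √(0.05 × 0.95/4000) = ±0.7 points. The mixture here has 8% preterm, term 3200 ± 430 g and preterm 2200 ± 500 g. The wider gap between term and preterm raises its rejection rate above that in Check 1.

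| Shape | AD by group (either) | AD on pair differences | Welch type I | Gated type I |
|---|---|---|---|---|
| Normal | 10% | 6% | 5.2% | 5.4% |
| Preterm mixture | 82% | 13% | 4.7% | 4.6% |
| Skew-normal | 98% | 9% | 5.2% | 5.1% |
| t, 5 df | 88% | 38% | 5.2% | 5.0% |
| Uniform (centile-like) | 100% | 12% | 4.7% | 4.7% |

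Over these five shapes plus lognormal and exponential, ungated Welch had type I error 4.5%-5.2% and power 0.79-0.82 at 0.311 SD, against 0.80 from the formula. A comparison of means at this size needs no normality check.

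**Pairing.** A paired test needs one partner per woman. The documents define no pairing, and the educated group may exceed 162, so one-to-one pairs need not exist.

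**The case against.** The case for leaving the rule alone is that it is a conventional two-step procedure that does no damage to error rates. Several parts of that case stand.

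- **The study's stated quantity is not lost.** A reader might infer that the rule could discard a mean difference the research question asks for. The documents do not support that. The question asks for the cohort's mean and SD, which Protocol section 7 reports whatever the check shows. A difference is only implied by the control role, and neither branch plans one.
- **Diversion to ranks is not shown to be likely.** The 47%-82% figures hold only for group-wise testing. A paired test's normality assumption concerns differences, where the rate is about 8%-11%. AD is also read with Q-Q plots, so it is not an automatic switch. The same points show that the branch is undefined.
- **Rounding is not an argument.** The documents mention no coarse rounding, and Protocol section 5.2 specifies digital scales. Normal weights rounded to 10 g or 50 g are rejected only about 5% and 9% of the time.
- **Neither test is uniformly more powerful.** If the preterm share fell from 14% to 6% (0.08 × 900 = 72 g), power would be about 25% for the t-test and 18% for rank-sum. Under a pure shift the rank test leads by about 1-3 points. Nothing in the documents says the effect of interest is confined to the low-weight tail, and preterm delivery and low birth weight are already secondary outcomes.

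What does not stand is the inference that the rule is harmless. Near-nominal error does not tell the reader in advance what will be compared, and the pairing error is unaffected.

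**Conclusion.** The concern holds as one of pre-specification and of the quantity tested. For both primary outcomes the choice between a means test and a rank test is left to a check with no threshold, no stated unit of testing and no rule for disagreement. At 162 per group that check gains no error control: Welch type I error is about 4%-6%, and the gated procedure is also near nominal.

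How often the analysis would move to ranks cannot be stated from the documents. It runs from about 8%-11% to about 47%-82% under the same 5%-12% preterm mixtures, depending on what is tested. These figures rest on assumed distributions and an assumed 5% AD level.

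GPT data collection ended on 25 June 2016 (Protocol section 1.1) and the SAP is dated 20 July 2016. A reader might infer that the test was left open with the results in view. The documents do not show this. They show only that one side of the comparison had been collected when the plan left the test undecided.

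**What to change.** In SAP section 6 and Protocol section 7:

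1. Delete the rule that lets the normality assessment choose the test.
2. Name one primary analysis for each continuous primary outcome (birth weight, customized centile): the unpaired difference in means, no education versus education, with 95% CI, by Welch t-test or a linear model with robust standard errors.
3. Replace the paired t-test and signed rank test with their two-sample counterparts.
4. Keep Q-Q plots as description, and give the unpaired Wilcoxon rank-sum test as a sensitivity analysis whatever the plots show.

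This follows the team's own practice at the GPT interim look (Protocol section 1.2), where a two-sample t-test was reported and a rank-sum test was used to confirm it.

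The cost is wording in two documents, plus about 1-3 points less power than the rank test if the true effect is a pure location shift.
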